1 TITLE

The BALANCED Anaesthesia Study is a prospective, randomised clinical trial of two levels of anaesthetic depth on patient outcome after major surgery.

2 RATIONALE

Delirium is a common and potentially serious complication for hospitalised elderly patients. It occurs after a wide variety of precipitating factors. Delirium is identified as a major challenge of perioperative care and identification of anaesthesia strategies to minimise its occurrence would have a major health benefit. Delirium is expensive both in terms of personal and economic cost. Moreover, the ageing demographic predicts that the incidence of delirium will increase greatly over the coming years. These poor outcomes lead to increased costs, and greater social and care giver burdens.

A surgical episode offers a unique opportunity in which to study delirium because it is a planned and predictable insult, which is known to result in this adverse outcome. Moreover, the high incidence of postoperative cognitive dysfunction (POCD) following major surgery makes this an appropriate high-risk group in which to investigate protective strategies for delirium.

This statistical analysis plan describes the analysis and reporting of the delirium sub-study of the BALANCED study. The delirium study was undertaken at 8 pre-specified centres within the BALANCED study.

3 STUDY DESIGN AND OBJECTIVES

3.1 Design

The Balanced study is an international multicentre, prospective, randomised, double blind (subjects, investigators and outcomes assessors), active control, parallel assessment, safety and efficacy study comparing bispectral index (BIS) target groups 50 and 35. At selected centres additional assessments for delirium and cognitive status were undertaken.

3.2 Primary Objective

To compare the post-operative incidence of delirium amongst patients undergoing major surgery between those randomised to a BIS of target 50 ('light' anaesthesia) compared with those randomised to a BIS of target 35 ('deep' anaesthesia).

Primary endpoint:

The incidence of post-operative delirium, defined as POD present at any of the 10 assessments over the 5 post-operative days. The 3

minute diagnostic interview for Confusion Assessment Method delirium (3D-CAM) or the CAM-ICU is used to determine the presence of delirium. This will be administered preoperatively and twice daily (05:00 -11:00 and 1800 – 2200) for 5 days postoperatively or until discharge. A modified version will be used for patients in ICU (CAM-ICU) who are unable to talk on these days. Delirium assessment will be performed when patients can be aroused sufficiently in order to be assessed for delirium (Richmond Agitation and Sedation Score >-4).

3.3 Secondary Objectives

- To quantify and compare the temporal pattern of the incidence of POD amongst patients undergoing major surgery between those randomised to a BIS of target 50 ('light' anaesthesia) compared with those randomised to a BIS of target 35 ('deep' anaesthesia).
- To quantify and compare the severity of POD amongst patients undergoing major surgery between those randomised to a BIS of target 50 ('light' anaesthesia) compared with those randomised to a BIS of target 35 ('deep' anaesthesia).
- To quantify and compare the change in cognitive function at discharge (or 7 days) post-operatively between randomised groups.
- To quantify and compare the change in cognitive function at 3 and 12 months post-operatively between randomised groups.
- To quantify and compare cognitive impairment at discharge (or 7 days), 3 and 12 months post-operatively between randomised groups.
- To test the associations between POD incidence and subsequent MMSE changes or cognitive impairment and AMTS levels at discharge, or 3 and 12 months.

Secondary endpoints:

1. The incidence of postoperative delirium (POD) on each of the 5 post-operative days.
2. The number of postoperative delirium (POD) episodes over the 5 post-operative days (as a measure of delirium severity).
3. Cognitive change as measured by the Mini-Mental State Examination (MMSE) score at discharge (or 7 days).
4. Cognition level as assessed by modified MMSE (Abbreviated Mental Test Score - AMTS) administered at 3 and 12 months postoperatively by telephone.
5. Cognitive impairment defined as a score on the Mini-Mental State Examination (MMSE) at discharge (or 7 days) as <26 or as an AMTS

score of <8 at 3 and 12 months. Calculated for those with a score ≥ 26 pre-operatively.

3.4 Exploratory Objectives

- To identify demographic, co-morbid and perioperative factors (including anaesthesia depth, BIS, MAP and MAC) that are independently associated with of delirium incidence.
- To identify demographic, co-morbid and perioperative factors (including anaesthesia depth, BIS, MAP and MAC) that are independently associated with severity of delirium.
- To identify demographic, co-morbid and perioperative factors (including anaesthesia depth, BIS, MAP and MAC) independently associated with changes in MMSE score and AMTS levels at 3 and 12 months.
- To test the association between any POD diagnosis and the clinical outcomes, any cardiovascular event (MI, cardiac arrest, stroke, PE) and any infection during 1 year follow-up.

4 GENERAL ANALYSIS DEFINITIONS

4.1 Treatment Allocation

Participants are randomised in a 1:1 ratio to a BIS of target 50 ('light' anaesthesia) or a BIS of target 35 ('deep' anaesthesia), with randomisation stratified by country.

4.2 Sample size calculation

Chan *et al.* showed that delirium incidence was reduced from 24.1% to 15.6% with the use of BIS-guided anaesthesia versus routine care in a broadly similar patient group to the BALANCED Study cohort, with the exception that 83% were ASA 1 or 2. Using the data from Chan *et al.* we hypothesise that the incidence of delirium will be reduced from 25% in the deep anaesthesia group (BIS target 35) to 15% in the light anaesthesia group (BIS target 50). A power analysis using this reduction from 25% to 15%, with power of 80% and two-tailed alpha = 0.05, indicates that approximately 270 patients are required in each group (total of 540 patients). We therefore plan to recruit approximately n=600 patients to allow for all-cause loss-to follow-up.

4.3 Participant populations

Approximately 600 participants from 8 sites in Australia, Hong Kong, USA and China will be enrolled in the study.

4.3.1 Intention-to-treat (ITT) population

All randomised participants participating in the sub-study who do not have a diagnosis of delirium pre-operatively will be included in the ITT population with treatment allocation based on randomised treatment. The primary and secondary endpoints will be analysed using the full analysis set population i.e. the intention-to-treat population which includes all randomised patients, without a pre-operative diagnosis of delirium undergoing induction of general anaesthesia for surgery.

4.3.2 Per-protocol population

The per-protocol (PP) population is defined as all randomised participants in the sub-study who meet all the inclusion/exclusion criteria for BALANCED with BIS group classified according to the actual median BIS value achieved irrespective of randomisation. Participants will be allocated to the BIS=50 group if the achieved median BIS is between 45 and 55 inclusive, and to the BIS=35 group if the achieved median BIS is between 30 and 40 inclusive. Participants who are not within these ranges will be excluded from these analyses. The primary and secondary endpoints will be compared between the two groups defined as per-protocol.

5 *DEMOGRAPHIC AND BASELINE CHARACTERISTICS*

Participant demographic and baseline clinical characteristics will be summarised descriptively by randomised group. Summaries will include frequencies and percentages for categorical data and means, medians, ranges, standard deviations and inter-quartile ranges as appropriate for continuous data. These baseline summaries will include the following variables:

- Age
- Weight
- Sex
- Ethnicity
- ASA physical status

- Charlson score
- WHODAS score
- Cancer diagnosis
- Emergency/elective surgery
- Surgery type
- Haemoglobin
- Albumin
- Creatinine
- Surgical duration
- Pre-operative MMSE

These data will be examined for any imbalances between randomised treatments. No formal hypothesis testing will be conducted on these baseline variables.

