7 EFFICACY ANALYSES

7.1 Primary endpoint analyses

The primary endpoint analysis will compare the primary endpoint, diagnosis of delirium at any post-operative assessment, in the intention-to-treat population, using a Mantel-Haenszel Chi-square test, stratified by study-centre groups. The pooled estimate of the odds ratio and 95% confidence interval from this analysis will be used to summarise the statistical comparison. Analyses will be undertaken on both the Intention-to-Treat population and the Per-Protocol populations.

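### The set labelled per-protocol groups patients by achieved BIS and not by randomised arm, so the analyses run beside ITT are as-treated comparisons adjusted for centre only

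*Combined protocol and SAP*

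**What the plan says.** Section 4.3.2 forms the two per-protocol groups "with BIS group classified according to the actual median BIS value achieved irrespective of randomisation". A median of 45 to 55 puts a patient in the BIS 50 group and a median of 30 to 40 in the BIS 35 group, whichever arm the patient was randomised to. For the rest, "Participants who are not within these ranges will be excluded from these analyses". That removes medians below 30, between 40 and 45, and above 55.

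Section 7.1 specifies the primary analysis in the ITT population and then adds: "Analyses will be undertaken on both the Intention-to-Treat population and the Per-Protocol populations". Section 7.2 repeats this for daily delirium incidence, delirium severity, MMSE change, AMTS level and cognitive impairment. Binary endpoints use a Mantel-Haenszel test stratified by centre group. Continuous endpoints use a linear model with group and centre. No patient-level covariate enters any of these analyses. Several paragraphs of section 7.2 name the randomised group as the factor and then say that the analysis is also run on the per-protocol set.

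Section 5 plans baseline tables by randomised group only. Section 4.3.1 limits ITT to patients "who do not have a diagnosis of delirium pre-operatively will be included in the ITT population"; section 4.3.2 does not repeat that restriction, but does require that the BALANCED eligibility criteria are met.

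**The concern.** A per-protocol set normally keeps each patient in the assigned arm and leaves out those who did not adhere. Here a patient randomised to BIS 35 with a median of 48 is analysed as BIS 50. Achieved BIS is measured after randomisation and may depend partly on the patient. If patients at higher risk of delirium run lower BIS values at the same target, they collect in the deep group, and light anaesthesia then looks protective without being so. That is the direction the trial hypothesises: "the incidence of delirium will be reduced from 25% in the deep anaesthesia group (BIS target 35) to 15% in the light anaesthesia group".

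The result would stand beside ITT under the per-protocol label and could be read as confirming it. A reader could not check the comparability of the achieved-BIS groups, because no baseline table is planned for them. There is also a programming ambiguity: section 7.2 calls the factor the randomised group, while under section 4.3.2 the per-protocol groups are not the randomised groups. Two programmers could produce different per-protocol results from the same text.

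**Working it through.** **1. The plan's own figure.** Inputs from section 4.2: 25% versus 15%, "with power of 80% and two-tailed alpha = 0.05". With pooled rate 0.20:

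n = [1.960 × √(2 × 0.20 × 0.80) + 0.842 × √(0.25 × 0.75 + 0.15 × 0.85)]² / 0.10² = 250 per group.

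Continuity correction: n′ = (n/4) × [1 + √(1 + 4/(n × 0.10))]² = 62.5 × (1 + √1.16)² ≈ 270 per group, 540 in total. This matches the plan, and 540/0.90 = 600 matches planned recruitment. The sample size is not in dispute; N = 600 is used below.

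**2. How many patients the rule drops or moves.** The documents give no distribution of achieved median BIS, so I assume a normal one. For an arm with mean m and SD s:

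- kept in own window = Φ((55 − m)/s) − Φ((45 − m)/s) for the BIS 50 arm
- moved to the other group = Φ((40 − m)/s) − Φ((30 − m)/s)

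The BIS 35 arm is the mirror image in every case shown.

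| Arm means, SD | Own window | Moved | Dropped |
|---|---|---|---|
| 50/35, SD 4 | 78.9% | 0.6% | 20.5% |
| 50/35, SD 5 | 68.3% | 2.3% | 29.5% |
| 50/35, SD 8 | 46.8% | 9.9% | 43.3% |
| 47/38, SD 5 | 60.1% | 8.0% | 31.9% |

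Percentages are of all randomised patients.

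**3. Size of the bias with no true effect.** Simulation: N = 600, about 20% delirium, no effect of depth. Assumptions: a latent frailty score correlated with achieved BIS at −0.3 to −0.5, raising the log-odds of delirium by 0.7 to 1.0 per SD. Odds ratios are light versus deep, so 1 is correct. Repeat runs differ by about 0.01 in odds ratio and 1-2 points in false-positive rate.

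| Arm means, SD | Log-odds slope | Current rule: OR | False positives | Randomised arm kept, own window only: OR | False positives |
|---|---|---|---|---|---|
| 50/35, SD 5 | 0.7-1.0 | 0.94-0.97 | about 5% | 0.99-1.01 | about 5% |
| 50/35, SD 8 | 0.7-1.0 | 0.76-0.90 | 6-17% | 0.99-1.01 | not tabulated |
| 47/38, SD 5 | 0.7 | 0.67-0.80 | 14-36% | 0.75-0.86 | 8-19% |

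At 47/38 with slope 1.0, the current rule reaches an odds ratio of about 0.59 and 58% false positives. ITT stayed at 0.98-1.01 throughout. With zero correlation the current rule gives about 1.00. With a correlation of +0.3 it gives about 1.25, a bias against light anaesthesia.

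**4. Why the last row differs.** On target, each window is centred on its arm mean, so it trims both tails equally and only the moved patients carry bias. At 47/38 the windows trim unevenly. The light arm loses mainly its low-BIS side and the deep arm mainly its high-BIS side. Under a negative correlation those are the frailer light patients and the fitter deep patients. Keeping the randomised arm removes the moved patients but not this uneven trimming.

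**The case against.** The strongest reply is that nothing confirmatory is at risk. Section 7.1 fixes the primary analysis in the ITT population, section 4.3.1 says the same for primary and secondary endpoints, and section 4.3.2 states the regrouping openly. This stands, and it is why the point is not graded higher. What is missing is an explicit ranking of the two analyses if they disagree.

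A reader might also infer the following, which the documents do not support:

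- *That the per-protocol analyses are unadjusted, or that every analysis has one.* All are stratified by centre or include it. The association of delirium with later cognition and the exploratory models in section 7.3 name no per-protocol version.
- *That a large bias favouring light anaesthesia is to be expected.* False-positive rates near 90% do appear in simulation, but only with arm means of 45/40 (a separation of 5 points against the 15 between the targets) and the strongest confounding assumed. No achieved mean, SD or correlation is in the documents. The sign of the bias is assumed too.
- *That prevalent delirium will be counted as post-operative.* Section 4.3.2 does omit the exclusion that section 4.3.1 states, but it requires the BALANCED eligibility criteria. These are not reproduced here and might cover it.
- *That restoring the randomised arm cures the problem.* The 47/38 row shows that it does not.

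Finally, section 7.3 already plans multivariable models with BIS and anaesthesia depth among the candidate factors. These are separate risk-factor models with data-driven selection; they do not adjust the per-protocol comparison.

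**Conclusion.** The point holds as a should-fix. The set in section 4.3.2 is an as-treated grouping under a per-protocol label. It is used beside ITT for the primary endpoint and each group-comparison secondary endpoint, with adjustment for centre only and a factor that section 7.2 misnames. That follows from the text and needs no assumption.

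The size of the bias does rest on assumptions. It ranges from negligible (arms on target, SD 5) to material (means 47/38, SD 5, slope 0.7), and its direction follows the sign of the frailty-BIS correlation. The figures show vulnerability, not an expected bias. The vulnerability grows as achieved separation shrinks, which is when a per-protocol analysis is most likely to be consulted. The ITT estimate, its error rate and its power are untouched.

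**What to change.** 1. In section 4.3.2, define the per-protocol set as ITT patients, with the same pre-operative delirium exclusion stated explicitly, who meet eligibility, are analysed in their randomised arm, and have an achieved median BIS within that arm's existing window.
2. Adjust that analysis for pre-specified covariates already listed in section 5: age, ASA status, Charlson score, pre-operative MMSE and surgery type. Label it supportive, with a caveat that selecting on achieved BIS can still bias it.
3. Move the achieved-BIS grouping to section 7.3 as an exploratory as-treated analysis, adjusted for the same covariates. Add a baseline table by achieved-BIS group, and make the factor named in section 7.2 agree with the set analysed.
4. State that conclusions rest on ITT if the results differ.

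The cost is SAP wording, one extra population flag and one extra table. The per-protocol set also shrinks, because patients in the other arm's window are dropped and not moved. In the 47/38 case it keeps 0.60 × 300 = 180 per arm. Power for 25% versus 15% is then 66%, against 87% with all 300 per arm (both without continuity correction). That is acceptable for a supportive analysis.

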7.2 Secondary endpoint analyses

The analysis of the secondary endpoint the incidence of POD at each assessment time will be undertaken as supporting analyses of the primary

endpoint. These analyses will compare POD between randomised groups at each post-operative assessment, in the intention-to-treat population, using a Mantel-Haenszel Chi-square test, stratified by study-centre groups. The pooled estimate of the odds ratio and 95% confidence interval from this analysis will be used to summarise the statistical comparison. Analyses will be undertaken on both the Intention-to-Treat population and the Per-Protocol populations.

The analysis of the secondary endpoint the severity of POD, in the intention-to-treat population, will be undertaken using a general linear model with study-centre and randomized groups as fixed factors in the model. The mean difference between randomised groups derived from the model will be presented with the 95% confidence interval. If the distribution of the severity does not meet the assumptions for this parametric analysis then the severity maybe square root transformed prior to analysis. Analyses will be undertaken on both the Intention-to-Treat population and the Per-Protocol populations.

The analysis of the secondary endpoint the change in MMSE score at discharge, in the intention-to-treat population, will be undertaken using a general linear model with randomised group and study-centre as fixed factors in the analysis. The mean difference in the changes between randomised groups derived from the model will be presented with the 95% confidence interval. Analyses will be undertaken on both the Intention-to-Treat population and the Per-Protocol populations.

The analysis of the secondary endpoint the AMTS level at 3 and 12 months, in the intention-to-treat population, will be undertaken using a general linear model with randomised group and study-centre as fixed factors in the analysis. The mean difference in the levels between randomised groups derived from the model will be presented with the 95% confidence interval. Analyses will be undertaken on both the Intention-to-Treat population and the Per-Protocol populations.

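### Section 4.3.2 labels as per-protocol what is an as-treated comparison: groups are set by achieved median BIS, not randomised arm, and compared with adjustment for centre only

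*Combined protocol and SAP*

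**What the plan says.** Section 4.3.2 assigns the BIS group by the value reached in theatre: patients are "classified according to the actual median BIS value achieved irrespective of randomisation". The rule is explicit: "Participants will be allocated to the BIS=50 group if the achieved median BIS is between 45 and 55 inclusive". The deep group is formed in the same way from medians of 30 to 40. Everyone else is dropped: "Participants who are not within these ranges will be excluded from these analyses". A patient randomised to BIS 35 with a median of 46 is therefore analysed as BIS 50, and one randomised to BIS 50 with a median of 39 is analysed as BIS 35.

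The section then says: "The primary and secondary endpoints will be compared between the two groups defined as per-protocol". Section 7.1 confirms this for the primary endpoint ("Analyses will be undertaken on both the Intention-to-Treat population and the Per-Protocol populations"), and Section 7.2 does the same for each between-group secondary endpoint. The methods are those used for ITT. Binary endpoints are analysed "using a Mantel-Haenszel Chi-square test, stratified by study-centre groups"; continuous endpoints use a linear model with group and centre. No patient-level covariate enters either. Section 5 tabulates baseline data by randomised group only.

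**The concern.** A per-protocol set normally keeps patients in their randomised arm and drops those who did not adhere. Here non-adherent patients can be moved to the other group. Achieved BIS is measured after randomisation and may reflect the patient's vulnerability and intraoperative course as well as the assigned target. If more vulnerable patients reach a lower BIS at the same target, they collect in the BIS 35 group, and their higher delirium risk looks like an effect of depth. That is the direction the trial hypothesises (25% deep, 15% light, Section 4.2). Centre adjustment does not address this, and the baseline tables would not reveal it.

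At stake is how the supporting results are read. Agreement between ITT and per-protocol, or a null ITT with a positive per-protocol result, would be taken as randomised evidence when half of that evidence is not.

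**Working it through.** **Plan's own figure.** The plan gives no number for the per-protocol set. Its sample size sets the arm size used below. For 25% vs 15%, 80% power and two-sided 0.05:

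- n = [1.960·√(2·0.20·0.80) + 0.842·√(0.25·0.75 + 0.15·0.85)]² / 0.10² = 250 per group.
- With continuity correction: (250/4)·[1 + √(1 + 4/(250·0.10))]² = 270 per group, as stated.

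**Inputs.** From the documents: bands 30–40 and 45–55; 1:1 allocation; 270 per arm; 20% delirium overall (midpoint of 25% and 15%). Assumed, because the documents are silent:

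- no true depth effect;
- achieved BIS normal within arm;
- vulnerability V doubles the odds of delirium per SD;
- V correlates -0.2 to -0.4 with achieved BIS at a given target.

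**Who is kept and who is moved.** For an arm with mean m and SD s, the share in a band (a, b) is Φ((b−m)/s) − Φ((a−m)/s).

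- Means 35/50, SD 5. Own band: Φ(1) − Φ(−1) = 0.683. Other arm's band: Φ(4) − Φ(2) = 0.023. Kept as written: 0.705 (71%); kept in own arm: 68%; cross-classified: 0.023/0.705 = 3%.
- Means 40/46, SD 7. Own band: 0.423 (deep) and 0.458 (light), average 0.440. Other band: 0.222 and 0.185, average 0.203. Kept as written: 64%; kept in own arm: 44%; cross-classified: 0.203/0.643 = 32%.

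**Bias under no depth effect.** Model: achieved BIS = m + s·(−r·V + √(1−r²)·noise), with r from 0.2 to 0.4, and logit(delirium) = constant + ln 2·V. Odds ratios are light vs deep; in each range the value further from the null is at the stronger correlation.

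| Achieved means, SD | Cross-classified | Kept: as written / own arm | Odds ratio as written | False-positive rate as written |
|---|---|---|---|---|
| 35/50, 5 | 3% | 71% / 68% | 0.96–0.98 | about 5% |
| 35/50, 7 | 12% | 60% / 52% | 0.89–0.94 | 5–7% |
| 38/47, 5 | 12% | 68% / 60% | 0.73–0.86 | 9–22% |
| 39/47, 6 | 21% | 66% / 52% | 0.70–0.84 | 10–27% |
| 40/46, 7 | 32% | 64% / 44% | 0.67–0.82 | 11–32% |

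ITT stays at about 5% in every row. For scale, the planned effect is an odds ratio of (0.15/0.85)/(0.25/0.75) = 0.53; a spurious 0.67 is ln 0.67/ln 0.53 = 63% of it on the log scale.

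**Own-arm rule in the same scenarios.** False-positive rates are about 5% in the first two rows. In the last three they are up to about 7% at correlation -0.2 and 12–14% at -0.4. Dropping patients on achieved BIS is still selection after randomisation. When the arms drift toward each other, the deep arm loses mainly its high-BIS tail and the light arm its low-BIS tail. Adding a baseline covariate correlated 0.7 with V (assumed) brings 38/47 and 39/47 to about 6%.

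**Sensitivity.** A separate simulation used 600 patients, 8 centres and the centre-stratified Mantel-Haenszel test.

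- V unrelated to achieved BIS: the rule as written was unbiased (odds ratio 0.99–1.01, false positives 4–6%).
- V lowering BIS by 2–4 points per SD and raising the odds of delirium 2–3 fold: 0.77–0.98 and 4–16% at means 35/50; 0.39–0.75 and 19–95% at means 39/47. The own-arm rule gave 4–6% and 11–64% respectively; ITT gave 3–7% throughout.

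**The case against.** The strongest reply is that nothing primary is at risk. Sections 4.3.1 and 7.1 place the primary analysis in the ITT population, and each between-group analysis in Section 7.2 names ITT first. The rule is also disclosed, with both bands given. This stands: a reader might infer that the trial's main result or its error rate is compromised, and the documents do not support that. What is missing is a statement that per-protocol is only supportive, and a label that says what the analysis is.

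A reader might also infer that Sections 7.1 and 7.2 contradict Section 4.3.2. They do not. Section 7.1 never names the randomised group as a factor. Section 7.2 does ("general linear model with study-centre and randomized groups as fixed factors in the model"), but in sentences about the ITT population. At most, Section 7.2 does not rename the factor for the per-protocol runs.

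Nor is the comparison wholly unadjusted, since centre is in every test or model; patient-level confounders are not.

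Finally, the size and even the direction of the bias are assumed. With means on target it is small under the main assumptions, and it vanishes if vulnerability does not affect achieved BIS. That also stands. But the plan cannot know beforehand that separation will be good, and poor separation is when readers turn to a per-protocol result.

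**Conclusion.** The point holds as one about the supporting analyses. The set defined in Section 4.3.2 is as-treated, its comparison is non-randomised, and only centre is adjusted for. The multivariable models in Section 7.3 are separate and do not repair it.

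Confidence is high on the definition and low on the size. Under the main assumptions the spurious odds ratio runs from about 0.89–0.98 (false positives 5–7%) with arms on target to about 0.67–0.86 (9–32%) with arms 3 to 6 points off target; stronger confounding gives more, and the opposite link between vulnerability and BIS would reverse the direction. It would be too strong to say that the per-protocol results will be biased, or that keeping patients in their own arm makes them unbiased.

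**What to change.** Amend before database lock, as Section 9 allows:

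1. In Section 4.3.2, define per-protocol as eligible patients whose median BIS lies in the plan's existing band for their own randomised arm, analysed in that arm. Patients in the other arm's band are excluded, not moved.
2. Adjust this analysis for age, ASA status, Charlson score and pre-operative MMSE, all listed in Section 5, alongside centre. For binary endpoints this means a logistic model in place of the Mantel-Haenszel test.
3. Tabulate baseline data for this set by arm.
4. Keep the achieved-BIS comparison only in Section 7.3, covariate-adjusted and labelled 'as-treated, non-randomised'.
5. State that ITT governs the conclusion and both other analyses are supportive, because exclusion on achieved BIS remains post-randomisation selection.
6. In Section 7.2, name the group factor used in the per-protocol runs.

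An instrumental-variable estimate in the ITT set, with randomised arm as instrument, is optional if the effect of achieved depth is wanted; it held false positives at about 5% in the main scenarios.

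The cost is wording and light programming, with no new data. The price is precision: the set falls from 71% to 68% of patients at means 35/50, SD 5, but from 64% to 44% at means 40/46, SD 7, with wider intervals.
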